BLQ	below level of quantification
BMI	Body Mass Index
BSA	body surface area
CV	coefficient of variation
DLQI	Dermatology Life Quality Index
DMC	Data Monitoring Committee
EAER	exposure adjusted event rate
EAIR	exposure adjusted incidence rate
ECG	electrocardiogram
ES	Enrolled Set
FAS	Full Analysis Set
GGT	gamma glutamyltransferase
HADS-A	Hospital Anxiety and Depression Scale-Anxiety
HADS-D	Hospital Anxiety and Depression Scale-Depression
HLGT	high level group term
HLT	high level term
IGA	Investigator's Global Assessment
LLQ	lower level of quantification
MAR	Missing at random
MedDRA	Medical Dictionary for Regulatory Activities
MCMC	Markov-Chain Monte Carlo
MCS	Mental Component Score
MI	multiple imputation
mNAPSI	modified Nail Psoriasis Severity Index
NRI	non-responder imputation
PASI	Psoriasis Area and Severity Index
PCS	Physical Component Score
PGADA	Patient's Global Assessment of Disease Activity
PK	pharmacokinetic
PK-PPS	Pharmacokinetic Per Protocol Set
PSSI	Psoriasis Scalp Severity Index
PT	preferred term
Q4W	every four weeks
SAP	Statistical Analysis Plan
SD	standard deviation
SF-36	Short Form 36 item Health Survey
SFU	Safety Follow-Up
SMQ	standard MedDRA query

SOC	system organ class
SOP	standard operating procedure
SS	Safety Set
TEAE	treatment-emergent adverse event
VAS	visual analog scale
WBC	white blood cell
WHO	World Health Organization

This document cannot be used to support any marketing authorization application and any extensions or variations thereof.

REDACTED COPY

1 INTRODUCTION

This statistical analysis plan (SAP) defines the summary tables, figures, and listings to be generated for the clinical study report and is based on the protocol amendment 1 (12 Aug 2016).

2 PROTOCOL SUMMARY

2.1 Study objectives

2.1.1 Primary objective

The primary objective of the study is to assess the long-term safety and tolerability of bimekizumab.

2.1.2 Secondary objective

The secondary objective of the study is to assess the efficacy of bimekizumab administered every four weeks (Q4W) over 48 weeks.

2.1.3 Other objectives

The other objectives of the study are to:

- Assess the pharmacokinetics (PKs) of bimekizumab
- Assess the immunogenicity of bimekizumab.

2.2 Study variable(s)

2.2.1 Safety variables

2.2.1.1 Primary safety variable

The primary safety variable is the incidence of treatment-emergent adverse events (TEAEs) adjusted by duration of subject exposure to treatment.

2.2.1.2 Other safety variables

Change from Baseline variables will be defined relative to the Baseline measurements from PS0011.

The other safety variables are:

- Change from Baseline in clinical laboratory values (chemistry, hematology, and urinalysis)
- Change from Baseline in vital signs
- Change from Baseline in physical examination
- Change from Baseline in 12-lead Electrocardiogram (ECG) results.

2.2.2 Pharmacokinetic variable

The PK variable is plasma concentrations of bimekizumab.

2.2.3 Immunological variable

The immunological variable is anti-bimekizumab antibody levels prior to and following study treatment.

2.2.4 Efficacy variables

Change from Baseline and responder variables will be defined relative to the PS0010 Baseline for subjects who are PS0010 Week 12 PASI90 responders and relative to both the PS0010 and PS0011 Baselines for subjects who are PS0010 Week 12 PASI90 non-responders).

2.2.4.1 Secondary efficacy variables

The secondary efficacy variables are:

- Psoriasis Area and Severity Index (PASI)90 response (defined as a subject that achieves 90% reduction in the PASI score from the Baseline of PS0010) over time
- Investigator's Global Assessment (IGA) response (Clear or Almost Clear with at least a 2 category improvement from Baseline on a 5-point scale) over time

2.2.4.2 Other efficacy variables

The efficacy variables detailed below will be evaluated at all scheduled visits in accordance with the Schedule of Assessment (see study protocol Table 5-1):

- PASI75 and PASI100 response
- Absolute and percent change from Baseline in PASI score
- Shift from PS0011 Baseline in IGA score
- Change from Baseline in Dermatology Life Quality Index (DLQI)
- Percent of subjects achieving a DLQI score of 0 or 1
- Absolute and percent change from Baseline in the body surface area (BSA) affected by psoriasis
- Change from Baseline in modified Nail Psoriasis Severity Index (mNAPSI) score (in the subgroup of subjects with psoriatic nail disease at Baseline)
- Change from Baseline in the Psoriasis Scalp Severity Index (PSSI) (in the subgroup of subjects with scalp psoriasis at Baseline)
- Change from Baseline in the Patient's Global Assessment of Disease Activity (PGADA) for the arthritis visual analog scale (VAS)
- Change from Baseline in Short Form 36 item Health Survey (SF-36) Physical Component Summary (PCS) score, Mental Component Summary (MCS) score, and individual domains
- Change from Baseline in the Hospital Anxiety and Depression Scale Anxiety (HADS-A) and Depression (HADS-D) scores
- Percentage of subjects with scores below 8 in HADS-A and HADS-D (subjects with normal scores).

2.3 Study design and conduct

2.3.1 Study description

This is a Phase 2b, multicenter, 48-week, double-blind, placebo-controlled, parallel-group extension study to assess the long-term safety, tolerability, and efficacy of bimekizumab administered subcutaneously in eligible adult subjects with moderate to severe chronic psoriasis who complete PS0010.

2.3.2 Study periods

This study will include two periods:

- Treatment Period (48 weeks)
- Safety Follow-Up (SFU) Period (20 weeks after the last dose of study medication).

Treatment Period

To be eligible to participate in this study:

- Subjects in PS0010 who received placebo or bimekizumab 64mg, 160mg, or 320mg loading dose + 160mg Q4W must achieve PASI90 response at Week 12 before entering PS0011 extension study on the same treatment dose
- Subjects who do not achieve PASI90 response at Week 12 in PS0010 while receiving placebo or bimekizumab 64mg Q4W will be assigned to receive bimekizumab 160mg on entering PS0011
- Subjects who do not achieve PASI90 response at Week 12 in PS0010 while receiving bimekizumab 160mg or 320mg loading dose + 160mg Q4W will be assigned to receive bimekizumab 320mg Q4W on entering PS0011
- Subjects who receive bimekizumab 320mg or 480mg Q4W in PS0010 will be assigned to receive bimekizumab 320mg Q4W on entering PS0011, regardless of their PASI90 response at Week 12 in PS0010.

Up to 240 subjects are anticipated to enroll in the study and the study medication will be administered in the clinic Q4W.

Subjects withdrawing early from the study will undergo the Early Withdrawal visit assessments and will enter the SFU Period.

Safety Follow-Up Period

Following completion or early withdrawal from the 48-week Treatment Period, subjects will return for a SFU visit 20 weeks after their last dose of study medication.

2.3.3 Study duration per subject

For each subject, the study is expected to last for a maximum of 64 weeks. This includes the following study period durations:

- Double-blind, placebo-controlled Treatment Period: up to 48 weeks
- SFU Period: 20 weeks after the last dose of study medication.

The end of the study is defined as the date of the last visit of the last subject in the study.

2.4 Determination of sample size

Up to 240 subjects are anticipated to enroll in PS0011. This number is based on the 240 subjects that are planned to be randomized in the feeder study, PS0010. The calculations to reach this sample size are outlined in the PS0010 protocol and SAP. As the primary objective of this study is to assess the long-term safety and tolerability of bimekizumab, the number of subjects anticipated is based on the number of subjects completing PS0010 and meeting eligibility requirements for PS0011.

3 DATA ANALYSIS CONSIDERATIONS

3.1 General presentation of summaries and analyses

Statistical analysis and generation of tables, figures, subject data listings, and statistical output will be performed using SAS Version 9.3 or higher. All tables and listings will use Courier New font size 9.

Descriptive statistics will be displayed to provide an overview of the study results. For categorical variables, the number and percentage of subjects in each category will be presented. Unless otherwise noted, all percentages will be displayed to one decimal place. No percentage will be displayed for zero counts, and no decimal will be presented when the percentage is 100%. For continuous variables, descriptive statistics will include number of subjects with available measurements (n), arithmetic mean, standard deviation (SD), median, minimum, and maximum. For bimekizumab PK concentrations, summary statistics will include geometric mean, geometric coefficient of variation (CV), 95% confidence interval for the geometric mean, median, minimum, and maximum. All summaries of PK variables will be based on the observed values. No imputation will be used.

Decimal places for descriptive statistics will always apply the following rules:

- “n” will be an integer
- Mean, SD, and median will use one additional decimal place compared to the original data
- CV[%] will be presented with one decimal place
- Minimum and maximum will have the same number of decimal places as the original value.

A complete set of data listings containing all documented data as well as calculated data (eg, change from Baseline) will be generated and will be presented by PS0010/PS0011 treatment group.

3.2 Definition of Baseline values

Two separate baseline values are defined for use in this study:

PS0010 Baseline

The last valid measurement before study medication administration in the double-blind period of PS0010 will be used as the PS0010 Baseline value. If a Baseline visit measurement is missing, and a PS0010 Screening visit measurement is available, the Screening value will be utilized as Baseline. If a scheduled Baseline assessment is taken on the same day as first administration of

PS0010 study medication, it will be assumed to have been taken prior to PS0010 study medication.

PS0011 Baseline

The last valid measurement before study medication administration in the double-blind period of PS0011 will be used as the PS0011 Baseline value. If a Baseline visit measurement is missing, the most recent PS0010 assessment value will be utilized as Baseline. If a scheduled Baseline assessment is taken on the same day as first administration of PS0011 study medication, it will be assumed to have been taken prior to PS0011 study medication.

3.3 Mapping of assessments performed at early study withdrawal visit

Study assessments at an early withdrawal visit where the early withdrawal visit date matches the visit date of a scheduled visit will be summarized at the scheduled visit with the same visit date. Premature withdrawal visit assessments that do not have a scheduled visit with a matching date will be assigned to the next scheduled site visit following the last visit where assessments were available. The only exception to this rule is for anti-Bimekizumab (BKZ) antibody assessments, where all premature withdrawal visit assessments will be assigned to the next scheduled visit at which anti-BKZ antibodies are assessed.

All by-visit summaries will contain nominal visits only. Unscheduled visits will not be mapped to scheduled visits.

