8.2 Week 4 (±3 days)

All procedures or assessments will be performed prior to administration of study drug, unless otherwise noted. The following procedures or assessments will be performed:

- Vital signs (blood pressure, pulse rate, and temperature)
- eC-SSRS
- PASI
- IGA

-
- DLQI
 - BSA
 - mNAPSI
 - PSSI
 - HADS
 - Obtain blood samples for:
 - Standard safety laboratory tests (hematology and biochemistry)
 - Bimekizumab plasma concentration
 - Anti-bimekizumab antibodies
 - Obtain urine sample for:
 - Urine pregnancy test for women of childbearing potential
 - Concomitant medications
 - Record AEs
 - Contact the IXRS
 - Study medication administration (after all other visit assessments are completed)

8.3 Week 8 (± 3 days); Week 16 (± 3 days); Week 32 (± 3 days); and Week 40 (± 3 days)

All procedures or assessments will be performed prior to administration of study drug (if applicable), unless otherwise noted. The following procedures or assessments will be performed:

- Vital signs (blood pressure, pulse rate, and temperature)
- eC-SSRS
- PASI
- IGA
- BSA
- HADS
- Obtain blood samples for:
 - Standard safety laboratory tests (hematology and biochemistry)
 - Bimekizumab plasma concentration (not collected at Week 32)
 - Anti-bimekizumab antibodies (not collected at Week 32)
- Obtain urine sample for:
 - Urine pregnancy test for women of childbearing potential

-
- Concomitant medications
 - Record AEs
 - Contact the IXRS
 - Study medication administration (after all other visit assessments are completed)

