8.10 Early Withdrawal Visit

Subjects withdrawing early from the study (see [Section 6.3](#)) will undergo the same assessments as the Week 48 Visit (see [Section 8.4](#)) and will enter the SFU Period.

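### SAP 3.3 places early-withdrawal values at the next site visit even where that scale or test is not planned there, and does not say how such values are then tabulated or imputed

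*SAP*

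**What the plan says.** SAP 3.3 gives two mapping rules for the early-withdrawal visit. If its date coincides with a scheduled visit, the assessments "will be summarized at the scheduled visit with the same visit date". If not, they "will be assigned to the next scheduled site visit following the last visit where assessments were available". It then adds: "The only exception to this rule is for anti-Bimekizumab (BKZ) antibody assessments". Unlike everything else, those "will be assigned to the next scheduled visit at which anti-BKZ antibodies are assessed". The section also says: "All by-visit summaries will contain nominal visits only".

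The withdrawal visit collects a full set of assessments. Under Protocol 8.10, subjects who leave early "will undergo the same assessments as the Week 48 Visit". (The cross-reference printed there leads to the Week 12 list, but the title of Section 8.8 and the last treatment column of Table 5-1 both put Week 48 and withdrawal together.) SAP 2.2.4.2 says the other efficacy variables "will be evaluated at all scheduled visits in accordance with the Schedule of Assessment", that is, Table 5-1.

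SAP 4.2.2 counts early discontinuers as non-responders for responder variables. Continuous variables are multiply imputed within treatment group from Baseline and post-Baseline visit values, with LOCF if the model does not converge. Protocol 6.3, criterion 12, requires withdrawal for PASI75 non-response at Week 12 or later.

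**The concern.** The rule looks at the site-visit calendar, not at the calendar of each assessment. A scale or test done every 12 weeks can therefore be placed at a visit where Table 5-1 plans no such measurement. The antibody exception shows that the SAP saw this problem for one assessment and left the rest on the general rule.

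If such a value has no row in the by-visit table and no column in the imputation model, the subject is represented by imputed values that ignore the last real observation. If a row is created for it instead, that row contains withdrawn subjects only. The summaries exposed are those meant to show maintenance of effect over 48 weeks in DLQI, mNAPSI, PSSI, PGADA and SF-36, and the by-visit tables for ECG, urinalysis and PK.

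**Working it through.** The documents give no figure on this point, so the check is a comparison of SAP 3.3 with Protocol Table 5-1.

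**1. Planned visits.** There are 12 post-Baseline site visits (Weeks 4 to 48, every 4 weeks). Nine come after Week 12: Weeks 16, 20, 24, 28, 32, 36, 40, 44 and 48.

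| Assessment | Planned at weeks | Not planned, of 12 | Not planned, of 9 after Week 12 |
|---|---|---|---|
| PASI, IGA, BSA, HADS, hematology/biochemistry, vital signs | all | 0 | 0 |
| DLQI, mNAPSI, PSSI | 4, 12, 24, 36, 48 | 12 − 5 = 7 (58%) | 9 − 3 = 6 |
| PGADA, SF-36, urinalysis | 12, 24, 36, 48 | 12 − 4 = 8 (67%) | 9 − 3 = 6 |
| ECG | 24, 48 | 12 − 2 = 10 (83%) | 9 − 2 = 7 |
| PK | 4, 8, 12, 16, 28, 40, 48 | 12 − 7 = 5 (42%) | 9 − 4 = 5 |

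**2. Can the rule be read more kindly?** If every assessment already went to its own next planned visit, the antibody exception would be redundant. A second reading takes the last visit with available data separately for each assessment, then moves to the next site visit. That does not help. Off-schedule targets are 4 of 5 for DLQI/mNAPSI/PSSI, 4 of 4 for PGADA/SF-36/urinalysis, 2 of 2 for ECG and 3 of 7 for PK.

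**3. Following a subject who fails PASI75 (the five scales).**
- Failure at Week 12: a same-day withdrawal visit maps to Week 12, which is planned. A later one maps to Week 16, which is not, but the Week 12 scales are already tabulated, so the affected value is close to a repeat.
- Failure at Week 16: a same-day visit maps to Week 16 and a later one to Week 20. Neither is planned.
- Failure at Week 20: a same-day visit maps to Week 20, not planned. A later one maps to Week 24, planned, or to Week 16, not planned, on the per-assessment reading in step 2.

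A subject failing at Week 16 or 20 must have met PASI75 at Week 12, or would already have been withdrawn. The last tabulated scales then date from a time of response, and the withdrawal value is the only one after the loss. The same pattern recurs between Weeks 24 and 36 and between Weeks 36 and 48.

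**4. PK against antibodies.** Table 5-1 gives both the same sampling visits. For a withdrawal mapped to Week 20, the antibody result goes to Week 28, while the PK result from the same visit goes to Week 20, where no PK is planned.

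**5. Imputation.** If the off-schedule value has no column, the model sees only the subject's earlier scores. It borrows later ones from subjects in the same treatment group who stayed in the study and, by criterion 12, still held PASI75. If LOCF is used, the SAP does not say whether the withdrawal value or the earlier planned one is carried forward.

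**6. Illustration.** Assume 240 subjects (the planned maximum) and withdrawals spread evenly over the 12 target visits. The number of off-schedule values is 240 × withdrawal rate × (not planned ÷ 12). At 10% for DLQI this is 24 × 7/12 = 14.

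| Withdrawal rate (assumed) | DLQI | SF-36 | ECG | PK |
|---|---|---|---|---|
| 5% (12 subjects) | 7 | 8 | 10 | 5 |
| 10% (24 subjects) | 14 | 16 | 20 | 10 |
| 20% (48 subjects) | 28 | 32 | 40 | 20 |

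**7. After the change.** With each assessment sent to its own next planned visit, off-schedule targets are 0 of 12 in every row. For DLQI, mNAPSI and PSSI, the 12 site visits map to Weeks 4, 12, 12, 24, 24, 24, 36, 36, 36, 48, 48 and 48.

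**The case against.** Four arguments on the other side carry weight.

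- **Loss is not stated.** Week 16 is itself a nominal visit, so restricting tables to nominal visits does not delete a value mapped there, and the date-match sentence says such values are summarized. A reader might infer that withdrawal data certainly disappear. The documents support only that their display and their use in imputation are unspecified.
- **No mix of reasons is given.** A reader might infer that the affected values come mostly from failing subjects and are the worst ones. PASI75 failure is one of 13 withdrawal criteria in Protocol 6.3, and neither document gives a withdrawal rate or a breakdown by reason.
- **Imputation uses the subject's own history.** Earlier poor scores still inform the model, so a Week 12 failure is largely covered. This does not help a subject whose earlier scores were all taken during response.
- **The reach is narrow.** The primary TEAE analysis does not use this mapping. PASI75/90/100, IGA, BSA, HADS, hematology/biochemistry and vital signs are collected at every site visit. DLQI 0/1 under non-responder imputation counts the subject as a non-responder wherever the value lands. ECG outlier counts use any post-dose assessment (SAP 8.2.5), urinalysis can still enter the End of Treatment shift table (SAP 8.2.2), all values are listed, and no inference is planned.

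These points limit the consequence. None of them supplies the missing rule.

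**Conclusion.** The gap is real and should be closed. As written, SAP 3.3 can send withdrawal values to visits where they are not planned: after Week 12, 6 of 9 visits for the five scales and urinalysis, 7 of 9 for ECG and 5 of 9 for PK. At the remaining visits the rule works, so this is not a universal loss.

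The likely result is omission from the by-visit and imputed summaries, or rows holding only withdrawn subjects. For the five scales, a bias towards maintained benefit is plausible where PASI75 is lost between planned scale visits, most clearly when failure is found at Week 16, 28 or 40, where both same-day and later withdrawal visits map off schedule. Its size cannot be estimated from the documents. The illustrative counts rest on assumed withdrawal rates and even spacing, and mandatory PASI75 withdrawal starting at Week 12 argues against even spacing. The secondary efficacy variables and the primary safety variable stand as planned.

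**What to change.** In SAP 3.3, replace the antibody exception with a general rule: any premature-withdrawal assessment that is not done at every visit goes to the next scheduled visit at which Table 5-1 plans it. Apply the same check to date-matched visits, so that a value is kept at the matched visit only if it is planned there. In SAP 4.2.2, state that the mapped value is used as observed in MI and in LOCF.

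The cost is a few sentences and a mapping by parameter, using logic the SAP already specifies for antibodies. The downside is that some values appear at a nominal week later than when they were taken: a scale completed soon after Week 12 would show at Week 24, and an ECG soon after Week 24 at Week 48. A table footnote can say so. For PK, where time since dose matters, the SAP may instead state that off-schedule withdrawal concentrations are listed only. If the general rule is not adopted, the SAP should at least say how off-schedule values are displayed and whether they enter MI and LOCF.

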3.4 Protocol deviations

Important protocol deviations are defined as those deviations from the protocol likely to have a meaningful impact on the efficacy, safety, or PK outcomes for an individual subject. The criteria for identifying important protocol deviations will be defined within the appropriate protocol-specific document. All protocol deviations will be reviewed as part of the ongoing data cleaning process and all important deviations will be identified and documented in a separate protocol deviation tracker prior to unblinding to confirm any exclusions from the Pharmacokinetics Per Protocol Set (PK-PPS).

3.5 Analysis sets

All safety variables will be summarized using the Safety Set (SS). All efficacy analyses will be based on the Full Analysis Set (FAS).

3.5.1 Enrolled Set

The Enrolled Set (ES) will consist of all subjects who have given informed consent for PS0011.

3.5.2 Safety Set

The SS will consist of all subjects who receive at least one dose of the study medication in PS0011.

3.5.3 Full Analysis Set

The FAS will consist of all enrolled subjects who receive at least one dose of the study medication in PS0011 and have a valid efficacy measurement for PASI at Baseline of PS0011.

3.5.4 Other analysis sets

3.5.4.1 Pharmacokinetics Per Protocol Set

The PK-PPS is a subset of the FAS, consisting of those subjects who had no important protocol deviations affecting the pharmacokinetic variables, as confirmed during ongoing data cleaning meetings prior to database lock.

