14.1 Definition of analysis sets

The Enrolled Set (ES) will consist of all subjects who have given informed consent for PS0011.

The Safety Set (SS) will consist of all subjects who receive at least 1 dose of the study medication in PS0011.

The Full Analysis Set (FAS) will consist of all enrolled subjects who receive at least 1 dose of the study medication in PS0011 and have a valid efficacy measurement for PASI at Baseline of PS0011.

The Pharmacokinetics Per-Protocol Set (PK-PPS) will consist of all enrolled subjects who receive at least 1 dose of the study medication in PS0011 and provide at least 1 quantifiable plasma concentration postdose in PS0011.

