14.5 Planned immunological analyses

Immunological variables will be analyzed for all subjects in the PK-PPS.

Anti-bimekizumab antibody data will be summarized by PS0010/PS0011 treatment group at each scheduled visit. The summary of anti-bimekizumab antibody levels will follow a similar approach to that used for the summary of bimekizumab plasma concentrations. Additional analyses related to antibody positivity will be performed and will be described in greater detail in the SAP.

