3.11 Changes to protocol-defined analyses

There have been no changes to the protocol-defined analyses.

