9.2 Immunogenicity

9.2.1 Anti-bimekizumab antibodies

Subjects with a positive on-treatment (i.e., excluding PS0010 Baseline) anti-BKZ antibody result in either PS0010 or PS0011 will be classified as anti-BKZ positive.

Anti-BKZ antibody status will be summarized for each PS0010/PS0011 treatment group at each scheduled PS0010 and PS0011 visit using the PK-PPS analysis set. The first occurrence of anti-BKZ antibody positivity will also be presented for each PS0010/PS0011 treatment group at each scheduled PS0010 and PS0011 visit.

The anti-BKZ antibody status will be determined for each visit where samples are taken for drug concentration means. The cut point for determining whether the anti-bimekizumab antibody level is sufficiently high to be considered anti-BKZ antibody positive is not yet known. However, this will be determined prior to the database lock of the PK and anti-BKZ antibody data.

A line plot of the percentage of anti-BKZ antibody positive subjects at each visit will be produced by PS0010/PS0011 treatment group. All individual subject-level anti-BKZ antibody results will be listed.

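### The PK-PPS has two non-nested definitions, the SAP declares no change, and the same set is the denominator for the antibody summaries

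*SAP*

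**What the plan says.** Protocol 14.1 builds the PK-PPS from enrolled subjects who are dosed in PS0011 and "provide at least 1 quantifiable plasma concentration postdose in PS0011". It sets no condition on protocol deviations or on PASI.

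SAP 3.5.4.1 says: "The PK-PPS is a subset of the FAS, consisting of those subjects who had no important protocol deviations affecting the pharmacokinetic variables". It has no concentration condition. Because the set sits inside the FAS, members must also "have a valid efficacy measurement for PASI at Baseline of PS0011" (SAP 3.5.3). On what counts as an important deviation, SAP 3.4 says: "The criteria for identifying important protocol deviations will be defined within the appropriate protocol-specific document". That document is not part of the protocol or SAP.

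On use of the set, protocol 14.5 says: "Immunological variables will be analyzed for all subjects in the PK-PPS". SAP 9.2.1 reports antibody status by PS0010/PS0011 treatment group and visit, "using the PK-PPS analysis set".

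On departures from the protocol, SAP 3.11 says: "There have been no changes to the protocol-defined analyses".

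**The concern.** One name refers to two different populations, and the SAP does not tell the reader that the definition moved. A programmer following the SAP and a reader following the protocol would expect different subjects in the PK and antibody tables.

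The antibody tables matter more. Assessing immunogenicity is a stated objective, listed among the other objectives in protocol 3.3 and SAP 2.1.3. The denominator for an antibody rate should be the subjects who were dosed and tested. Here it depends on something else under either rule:

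- Under the protocol rule, membership depends on a drug level measured after baseline. If antibodies kept a subject's drug unmeasurable throughout, the outcome being counted would have removed that subject from the count.
- Under the SAP rule, membership depends on PK-relevant deviations and on a Baseline PASI. Neither document says why either should invalidate an antibody result.

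**Working it through.** No figure in the plan rests on this definition, so there is none to reproduce. The check is a comparison of membership, followed by the arithmetic of how exclusions move a rate.

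**Step 1: membership.** Take subjects dosed in PS0011 and cross the three conditions that the two definitions use (protocol 14.1; SAP 3.5.3 and 3.5.4.1).

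| Valid PS0011 Baseline PASI | Any measurable postdose level | Important PK deviation | Protocol | SAP |
|---|---|---|---|---|
| yes | yes | no | in | in |
| yes | yes | yes | in | **out** |
| yes | no | no | out | **in** |
| yes | no | yes | out | out |
| no | yes | no | in | **out** |
| no | yes | yes | in | **out** |
| no | no | no | out | out |
| no | no | yes | out | out |

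The rules disagree in 3 + 1 = 4 of 8 rows: three are in under the protocol and out under the SAP, and one is the reverse. The sets are therefore not nested. These are logical combinations, not expected frequencies.

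**Step 2: is the SAP wording merely shorthand?** It does not read that way. SAP 3.4 and 5.2 both describe exclusion from the PK-PPS in terms of important deviations, and neither mentions a measurable sample. SAP 9.1 sets concentrations below quantification to half the lower limit and keeps them, which fits a set without a concentration rule.

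**Step 3: consequence for a planned table.** SAP 3.6 lists Placebo to Placebo as a reporting group, and SAP 9.2.1 gives antibody status for each such group. These subjects receive placebo in both studies, so no measurable bimekizumab is expected. The protocol rule should leave that column essentially empty; the SAP rule can populate it.

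**Step 4: how narrow is the protocol-rule mechanism?** Protocol Table 5-1 schedules postdose samples at Weeks 4, 8, 12, 16, 28, 40, 48 and SFU, which is 8 for a completer. A single measurable value keeps the subject in. Only a subject with none is lost. Early withdrawals have fewer samples, so the risk is higher for them but still confined to subjects with no measurable value.

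**Step 5: direction.** Let p be the true antibody-positive share, f the share of positives excluded and g the share of negatives excluded. The reported rate is p(1 − f) / [p(1 − f) + (1 − p)(1 − g)]. It falls when f > g and rises when g > f. With assumed values, none of them from the documents:

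- p = 10%, f = 25%, g = 0: 0.075 / (0.075 + 0.90) = 7.7%.
- p = 10%, f = 0, g = 25%: 0.10 / (0.10 + 0.675) = 12.9%.

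The documents give no value for p, f or g under either rule, so these lines show only that the sign is open.

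**The case against.** The strongest reply is that this is a documentation mismatch with little practical effect. Much of that stands. The study is descriptive, with no inferential analysis planned (protocol 14.2). SAP 9.2.1 lists every individual antibody result. Adverse events by antibody status are summarised on the Safety Set (SAP 8 and 8.2.1), and efficacy by antibody positivity on the FAS (SAP 4.7). SAP 5.1 and 5.2 tabulate the size of each analysis set and the PK-PPS exclusions due to deviations. Protocol and SAP also agree with each other that antibodies go on the PK-PPS, so moving them is an improvement in the choice of set rather than the repair of a contradiction.

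Three stronger readings are tempting, and the documents do not support them:

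- A reader might infer that both definitions remove the subjects most likely to be antibody positive. The drug-clearance mechanism belongs to the protocol rule alone. The SAP set has no concentration condition, so a subject whose drug was cleared stays in. Nothing in either document says that subjects with PK deviations are more often antibody positive, and the deviation criteria are held elsewhere.
- A reader might infer that the rule on dosing 7 days out of window discards antibody data. In SAP 5.2 and 9.1 it removes plasma concentrations from the PK summary. It is not written as removing subjects or antibody results.
- A reader might infer that the antibody rate will be understated. That needs positives to be excluded more often than negatives, which the documents do not establish.

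The reply does not dispose of the undeclared change of definition. Nor do the listings correct the summarised rate: a subject can be counted as antibody positive in the safety and efficacy tables and be absent from the antibody incidence table.

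**Conclusion.** The inconsistency is certain on the text: two non-nested rules under one name, with SAP 3.11 stating that nothing changed. It is also certain that the antibody denominator depends on whichever rule is applied, including whether the Placebo to Placebo column has any subjects.

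The numerical effect on the antibody rate is unknown in size and direction. Under the protocol rule it is probably small, because a subject must have no measurable postdose sample at all. Under the SAP rule it depends on deviation criteria that neither document contains. The point is worth correcting because immunogenicity is an objective and the correction is cheap, not because bias has been shown. It rests on reading both definitions literally; if an unstated concentration rule is meant to apply in the SAP, the SAP needs to say so.

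**What to change.** 1. In SAP 9.2.1, summarise anti-bimekizumab antibody status on Safety Set subjects with at least one antibody result in PS0011. This matches the set already used for adverse events by antibody status.
2. In SAP 3.5.4.1, give one PK-PPS definition for the PK summaries and name that set in SAP 9.1, which currently names none. The definition should be consistent with keeping values below quantification at half the limit. Reinstating the protocol's concentration rule is a debatable choice, because it would remove exactly the subjects whose values are all below quantification and so select on the quantity being summarised.
3. In SAP 3.11, replace the statement of no changes with an entry for each of these two departures from protocol 14.1 and 14.5, with a reason.

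The cost is SAP wording and one population flag. No data collection or trial conduct changes.
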